10.3. Local Skin Reactions

Local skin reactions (LSRs) to treatment reported by investigators and subjects will be recorded as adverse events. LSRs will include adverse events taking place at the site of study drug administration such as, blistering, pain, pruritus, burning, erythema, edema/swelling, erosion/ulcerations, flaking/scaling/dryness, scabbing/crusting, scarring, ring wart, and pigmentation changes. These events of interest are denoted on the CRF by the investigator as events occurring at a location where drug was administered. These will be mapped to the appropriate MedDRA classification and summarized using similar methods as described in Section 10.2 for adverse events.

Summaries of LSRs will include the following:

- Subject count and incidence rate of LSRs by MedDRA system organ class and preferred term.
- Subject count and incidence rate of LSRs by MedDRA system organ class, preferred term and highest severity. At each level of subject summarization, a subject is classified according to the highest severity if the subject reported one or more events.

- Subject count and incidence rate of LSRs by MedDRA system organ class, preferred term and closest relationship to study drug (Related/Not Related). Related LSRs are those reported as “Definitely”, “Probable” or “Possibly”. At each level of subject summarization, a subject is classified according to the closest relationship if the subject reported one or more events. LSRs with missing relationship will be considered related for this summary.
- Subject count and incidence rate of serious LSRs by MedDRA system organ class and preferred term.
- Subject count and incidence rate of LSRs by MedDRA system organ class and preferred term by gender

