6.1.3 Part A and Part B Procedures

6.1.3.1 Subject Participation

Pre-study screening for eligibility (informed consent, demographics, physical exam, vital signs, prior and concomitant medications, and medical history) can occur up to 14 days before, or on the same day as Treatment Visit 1. The dermatologic exam, wart count, wart measurement (diameter), location of all warts, and photographs (if applicable) must be repeated at Treatment Visit 1 if the Screening Visit is not conducted on the same day. Warts must measure ≤ 8 mm in diameter each with a total wart area (i.e., all warts combined) ≥ 10 mm² at baseline. Wart count must be ≥ 2 and ≤ 30 total warts within the allowed treatment areas at the time of Treatment Visit 1.

Subjects who do not continue to meet criteria at Treatment Visit 1 will be considered a screen failure and will be treated at physician discretion per standard of care. Subjects who meet the enrollment criteria will be randomized to receive VP-102 or placebo. Treatment will continue with a minimum of every 21 ± 4 days, until complete clearance or a maximum of four treatment sessions. The exact treatment interval will be determined by evaluation of the treatment site and take any ongoing LSRs into account. Subjects who achieve complete clearance of all treatable warts before Treatment Visit 4 will be required to return for every scheduled, in-person, treatment and follow-up visit, whether or not their warts have cleared. The 24-hour, 7-day, and 14-day evaluation of response to treatment (ERT) telephone follow-ups will be conducted per protocol for those instances in which the subject was treated.

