6.1.3.2 Efficacy Procedures

All required study activities, including an ERT (i.e., assessment of wart activity [count, location, diameter] and related LSRs), will be conducted per protocol. A Blinded Assessor will perform wart counts before the ERT assessment at Treatment Visit 2, Treatment Visit 3, Treatment Visit 4, End of Treatment Visit, and Follow-up Visit.

Treatment visits are to take place in order (i.e., Treatment 1, Treatment 2, Treatment 3, and Treatment 4). All subjects will receive application of study drug to EGW, including an approximate margin of healthy surrounding skin, at an interval of every 21 ± 4 days until complete clearance of all treatable warts, or a maximum of four applications.

No partial treatment of warts (e.g., treating one wart and not another) is permitted. In any instance where the clinician is uncertain if a residual wart is remaining, treatment should be applied. Instructions for application of the study drug are outlined in the Instructions for Use included in the drug shipment, as well as included in the Site Regulatory Packet.

Subjects should be re-treated only after 17 to 25 days (i.e., 21 ± 4 days) have elapsed since the previous treatment and only after any LSRs have resolved sufficiently to allow evaluation of the treatment site. Treatment should only take place at a visit when all warts are evaluable (i.e., not obscured by an ongoing LSR). All warts that are not completely clear should undergo treatment with study drug. Subjects exhibiting skin reactions that need additional time, at the Investigator's discretion, before they can be treated again will be evaluated and asked to return for their next treatment visit after the area is considered sufficiently resolved to allow for the next treatment (e.g., ongoing dryness or erythema is appropriate to treat). See instructions below regarding unscheduled visits.

Subjects who receive <4 treatments within the treatment period, or have visits that are outside of the visit window due to the duration of post-treatment LSRs, will not be considered a protocol deviation. In the event that a subject misses a treatment visit, and is outside the 4-day study window, they may return and be treated at the next available opportunity with the subsequent visit scheduled 21 ± 4 days after the actual treatment visit. No treatment should be administered after the treatment period without the Sponsor's approval.

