On the Wart Count case report form (CRF), the total number of overall EGW warts is collected. Genital warts that develop in areas that are unable to be treated or other types of warts will not be evaluated, documented, or considered in the analysis.

Some efficacy endpoints will be summarized by treatment visit. Treatments are planned to occur every 21 (+/- 4) days as long as warts are present for up to 4 treatments within the 75 day treatment period. Treatment may be delayed for various reasons, including but not limited to ongoing LSRs. As a result, the timing of when subjects receive treatment may vary. For the purpose of summarizing treatment visits, only visits when treatment was given will be considered. Moreover, a window will be applied to each visit to ensure that subjects are compared at the same treatment durations. A window of +/- 10 days from the targeted treatment schedule will be used. The table below summarizes the windows. These windows will be used on all by-visit summaries.

Visit	Target Day	Window
1	1	N/A
2	21	11 – 31
3	42	32 – 52
4	63	53 – 73
Day 84 EOT	84	74 – 94
Follow-up Day 112	112	95 – 129
Follow-up Day 147	147	130 – 157

If more than one visit falls within a window, then the visit closest to the target day will be used in the analysis. Visits when treatment was planned but treatment was not applied will be recorded as “Unscheduled”. Unscheduled visit information will not be considered for by-treatment visit summary tables. However, all efficacy data will be presented in data listings.

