10.4. Evaluation of Response to Treatment (ERT)

For each treatment visit, an Evaluation of Response to Treatment (ERT) will be performed (in clinic) at each visit, including 48 hours after first dose in Part A only and 24-hour, 7 Day, and 14 Day post treatment (by phone). ERT data will be presented in listings.

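### SAP 10.3 tabulates local skin reactions only as whole-study subject incidence, so reaction risk per application is mixed with the number of applications each arm received

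*SAP*

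**What the plan says.** SAP 10.3 lists five LSR summaries. The basic one is "Subject count and incidence rate of LSRs by MedDRA system organ class and preferred term". The severity table is "Subject count and incidence rate of LSRs by MedDRA system organ class, preferred term and highest severity". The others are by closest relationship to study drug, serious LSRs, and by gender. In the severity table, "a subject is classified according to the highest severity if the subject reported one or more events". None has a visit, treatment-period or application dimension.

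The number of applications is not fixed. Protocol 6.1.3.1 continues treatment "until complete clearance or a maximum of four treatment sessions". The introduction to SAP Section 8 adds: "Treatment may be delayed for various reasons, including but not limited to ongoing LSRs". Protocol 6.1.3.2 accepts fewer than four treatments, and says that visits "outside of the visit window due to the duration of post-treatment LSRs, will not be considered a protocol deviation". Protocol 6.4 allows no treatment after Day 75 unless the sponsor approves.

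Reactions are collected after each application, by telephone at 24 hours, 7 days and 14 days, on the Evaluation of Response to Treatment (ERT) form. SAP 10.4 states that "ERT data will be presented in listings". SAP 10.1 displays the numbers of treatment visits and warts treated but does not link them to LSRs. Protocol 12.4 mentions a count of treatment-emergent events by treatment, but also counts each event once per subject. The adverse event bullets in SAP 10.2 contain subject counts only.

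**The concern.** Part B's primary objective is to identify the regimen with the better balance of risk and benefit, and LSRs are the main tolerability data. Subjects who clear early have fewer applications after which a reaction can be recorded. If one arm clears sooner than another, its whole-study LSR incidence falls for that reason alone. A reader of the planned tables cannot tell whether a lower figure means a milder reaction per application or fewer applications.

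The same applies to VP-102 against placebo. If placebo subjects clear less often and so receive more applications, the excess of LSRs on VP-102 per application is understated.

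**Working it through.** The documents give no LSR rate, no distribution of applications and no power figure, so there is no plan figure to reproduce. What follows is an illustration with assumed rates.

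**1. Can delay remove an application?** Day 1 plus 21-day intervals gives Days 1, 22, 43 and 64, which leaves 75 − 64 = 11 days of total delay. At the longest permitted interval of 25 days, the applications fall on Days 1, 26, 51 and 76, so the fourth passes Day 75. Delay can therefore cost an application, but only once it totals more than 11 days on the 21-day schedule, and the sponsor may approve later treatment.

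**2. Cumulative incidence, independent applications.** With risk p per application (assumed), P(at least one in k) = 1 − (1 − p)^k.

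| p | k=1 | k=2 | k=3 | k=4 |
|---|---|---|---|---|
| 10% | 10.0% | 19.0% | 27.1% | 34.4% |
| 20% | 20.0% | 36.0% | 48.8% | 59.0% |
| 30% | 30.0% | 51.0% | 65.7% | 76.0% |
| 80% | 80.0% | 96.0% | 99.2% | 99.8% |

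**3. Half of one arm stops after two; all of the other receive four (assumed).**
- p = 20%: 0.5 × 36.0 + 0.5 × 59.04 = 47.5%, against 59.0%. Gap 11.5 points with identical risk per application.
- p = 10%: 26.7% against 34.4%. Gap 7.7 points.
- p = 30%: 63.5% against 76.0%. Gap 12.5 points.
- p = 80%: 97.9% against 99.8%. Gap 1.9 points.

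**4. Within-subject correlation.** If some subjects are prone to react and others are not, repeated applications add less. With a beta-binomial and intraclass correlation ρ (assumed), put s = 1/ρ − 1 and b = (1 − p)s. Then P(at least one in k) = 1 − Π (b + j)/(s + j), for j = 0 to k − 1.
- p = 20%, ρ = 0.5: s = 1, b = 0.8. For k = 2, 1 − 0.8 × 0.9 = 28.0%. For k = 4, 1 − 0.72 × (2.8/3) × (3.8/4) = 36.2%. The half-and-half arm shows 32.1%. Gap 4.1 points.
- p = 20%, ρ = 0.8: 23.2% and 26.1%; half-and-half 24.6%. Gap 1.4 points.

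**5. Can the order of two arms reverse?** Compare 25% per application with half stopping after two against 20% with all receiving four.
- ρ = 0: 56.1% against 59.0%. The arm with the higher risk per application looks milder.
- ρ = 0.2: 48.6% against 48.4%. The reversal has gone.
- ρ = 0.5: 39.0% against 36.2%. The order is correct.

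**The case against.** The best defence is that whole-course incidence is a legitimate measure. The regimen under study is up to four applications, stopping at clearance. A regimen that clears sooner does spare subjects later reactions, and that is real patient burden. This stands: the whole-study tables should stay, and first-application reactions should not replace them.

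The stakes are also modest. SAP 8.6 calls all comparisons exploratory, and Protocol 12.3 treats comparisons across regimens as observational. With about 27 VP-102 subjects per regimen in Part B (3/10 of 90), 11.5 points is about three subjects. A 95% interval for the difference is about ±1.96 × √(0.475 × 0.525/27 + 0.59 × 0.41/27) = ±26 points. This limits the consequence, but the missing breakdown remains. Part A's review after one application, at 48 hours, has no counterpart in the planned LSR tables.

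A reader might infer three stronger things that the documents do not support:
- **That LSRs are reported only as each subject's worst event.** Highest severity governs one table of five. The basic, serious and gender tables count any occurrence, and one uses closest relationship.
- **That the tables show fewer reactions than a regimen causes per application.** This cannot happen, because 1 − (1 − p)^k is never below p. The understatement is relative to an arm given more applications.
- **That poor tolerability lowers its own measured risk through delays.** A subject whose LSR delays retreatment is already counted for that LSR. A lost later application can hide only other reactions or a higher grade.

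**Conclusion.** The point holds in a limited form. No planned LSR table separates reaction risk per application from the number of applications, which can differ between arms mainly through early clearance and to a lesser degree through delay and the Day 75 limit.

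The distortion is conditional. At 20% per application, with half of one arm stopping after two and none of the other, it runs from 11.5 points under independence to 1.4 points at a correlation of 0.8. It is small for near-universal reactions, which may include blistering, since Protocol 6.1.1 requires it in most patients. It matters most for less common or more severe LSRs. A reversed ranking of regimens is possible but should not be presumed: in the example it needs a correlation below about 0.2. The rates, the correlation and the split of applications are all assumptions. Whether the arms will differ in number of applications cannot be known from the documents.

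**What to change.** Add to SAP 10.3 a descriptive table, by arm, of LSR incidence and worst severity by application number (1 to 4), with subjects treated at that application as the denominator. Present it beside the whole-study tables, not in place of them.

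- Assign reactions and severity from ERT records as well as adverse event onset dates. Protocol 10.3 records an event at the highest intensity of its whole course, and Protocol 6.1.3.2 allows retreatment over ongoing dryness or erythema. Onset date alone could therefore credit the first application with a grade reached after the second.
- Read the first-application row as the comparison with equal application counts. It is equal in count only, since subjects may enter with 2 to 30 warts.
- Footnote that later rows exclude subjects who are already clear, so they are selected groups.

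The cost is one or two extra tables from data already collected, with no protocol change. The drawback is small, selected denominators at later applications.

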- b. The ERT telephone calls should be conducted based on the time of study drug application. The ERT telephone calls at 24 hours (± 6 hours), 7 days (± 24 hours), and 14 days (± 24 hours) after each treatment visit are not required if there was no treatment during that treatment period. The ERT telephone call at 24 hours (± 6 hours), 7 days (± 24 hours), and 14 days (± 24 hours) after each treatment will only collect information since the last contact.
- c. All treatments may be administered over the course of up to 75 days. Provider questionnaire to be completed at the Study Day 84 (EOT) Visit by a clinician who applied treatment to the subject during the course of the study.
- d. In the event that any post-treatment LSR AE presents a safety concern (including but not limited to severe blistering, ulceration, edema, or pain), an “Unscheduled” clinic visit must be scheduled and the subject assessed accordingly. In addition, if any post-treatment AEs present a safety concern, the subject may be brought in for an unscheduled visit. “Unscheduled” visits should also be used for visits in which treatment is unable to be applied to all warts due to ongoing LSRs.
- e. Subjects are to be scheduled in 21 (± 4)-day intervals after each treatment. The next treatment visit is to be scheduled 21 (± 4) days after the last treatment, but only after any LSR has resolved sufficiently to allow evaluation of the treatment site. The research team should be in contact with the patient until LSRs are resolved and a treatment visit can be scheduled within 21 days (± 4) when possible.
- f. Subjects will return for additional Follow-up Visits on Study Day 112 (± 7 days) and Study Day 147 (± 7 days) (EOS) for an assessment of warts to determine the durability of previous responses and/or LSRs. Subjects are to attend all planned in-person visits, whether they have achieved complete clearance before or at the Study Day 84 ($-0/+8$ days) EOT assessment.
- g. Demographics: date of birth, sex, race, and ethnicity will be collected.
- h. Vital signs (e.g., temperature, heart rate) will be obtained at each treatment visit before application of study drug.
- i. Additional limited physical examination, symptom, or AE-directed physical examination may be performed if warranted (see Source/eCRF for a more detailed description)

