Treatment with VP-102 was well-tolerated. A total of 29 subjects (88%) reported at least one treatment-emergent adverse event (TEAE), including expected LSRs such as blistering or erythema. Most subjects had mild TEAEs; 3 subjects had moderate TEAEs. Overall, 21 (63.6%) subjects had TEAEs related to study drug, most of which were LSRs. There were no serious adverse events (SAEs) or TEAEs leading to premature study withdrawal.

Treatment with VP-102 was associated with significantly reduced lesion count, improved QoL, and complete clearance of MC lesions. Sixteen (16) subjects (48.5%) achieved complete clearance of all MC lesions on or before Week 12. The median lesion count was reduced 98% from baseline to Week 12. Decreases in mean CDLQI composite scores were observed, from 2.58 (standard deviation = 3.446) at baseline to

0.38 (standard deviation =0.871) at Week 12. No subjects reported spread of molluscum lesions to any siblings during the study.

Plasma drug levels were below the limit of quantitation in 65 of 66 samples. In one subject, the level was slightly above the lower limit of quantitation 2 hours after VP-102 application but was not detectable at 6 and 24 hours. Importantly, no systemic cantharidin was detected in the patient with the highest number of lesions (113 lesions treated) nor in the two subjects with genital involvement.

In a separate double-blind, Phase 2 study (12-01-004), topical cantharidin (0.7% w/v) was well tolerated and associated with the clearance of MC in 94 subjects with childhood molluscum.^[15]

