6.1.1 Part A (dose regimen finding) Study Design

The aim of Part A is to determine the two best treatment regimens for evaluation of safety and efficacy in Part B.

Treatment regimens will be evaluated based on the requirement to form blisters in most patients, while maintaining a favorable safety and tolerability profile (e.g., majority of LSR AEs are mild or moderate in severity). Accordingly, increasing durations of skin exposure to study drug (VP-102 or placebo) will be evaluated in three treatment groups (n=6/group) that will enroll progressively.

Subjects will have a Screening Period of up to 14 days before the first treatment, followed by a Treatment Period starting at Treatment Visit 1 and lasting through Treatment Visit 4.

Eighteen (18) subjects at up to six sites (additional sites may be added if required to ensure successful recruitment of the study population) will be enrolled, into either the 2-hour (Group 1), 6-hour (Group 2), or 24-hour (Group 3) treatment duration of skin exposure groups (n=6 subjects/group). Each group will include a minimum of two subjects from each sex and will be randomized 5:1 (VP-102:placebo) within each group. All subjects will receive either VP-102 (containing 0.7% cantharidin [w/v] topical film-forming solution) or placebo. Warts are to be treated and then covered (unless prohibited by wart location) with transparent surgical tape (e.g., 3M™ Blenderm™ brand) that will remain on the skin until the designated time for removal. Subjects will be asked to remove the surgical tape and study drug with soap and water after the pre-determined duration of skin exposure for their group.

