12.4 Safety Analyses

Safety analyses will be conducted in the Safety Population by actual treatment received.

Adverse events, including LSRs, will be coded with the Medical Dictionary for Regulatory Activities (MedDRA[®]) Version 20.0. The number and percentage of subjects having TEAEs will be tabulated by system organ class and MedDRA preferred term with a breakdown by treatment group. A subject-by-subject AEs data listing, including verbatim term, preferred term, treatment, severity, location, and causal relationship to the study drug will be provided. The number of subjects experiencing TEAEs and number of TEAEs will be summarized by treatment using frequency counts.

Any AE with an onset date after the EOS visit will be considered off study and will not be included in tables summaries (although they will appear in AE listings). Each AE will be counted only once for a given subject. If the same AE occurs on multiple occasions for a subject, the occurrence with the highest severity and relationship to study drug will be reported. If two or more AEs are reported as a unit, the individual terms will be reported as separate events.

Changes in vital signs (temperature and heart rate), from baseline to EOS, will be examined. Treatment-emergent changes from normal values to abnormal values will be identified.

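### No planned table shows how long local skin reactions last or whether they persist to the end of follow-up, although Part B must choose a regimen on risk:benefit

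*SAP*

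**What the plan says.** SAP 10.3 treats LSRs as adverse events, "summarized using similar methods as described in Section 10.2 for adverse events". It lists five summaries: by preferred term, by highest severity ("Subject count and incidence rate of LSRs by MedDRA system organ class, preferred term and highest severity"), by closest relationship to study drug, serious LSRs, and by gender. All five are subject counts and incidence rates. Within a subject the rule is: "At each level of subject summarization, a subject is classified according to the highest severity if the subject reported one or more events". Protocol 12.4 collapses repeats in the same way: "If the same AE occurs on multiple occasions for a subject, the occurrence with the highest severity and relationship to study drug will be reported".

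SAP 10.4 covers the repeated skin assessments in one line: "ERT data will be presented in listings".

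Four other places bear on duration.
- Protocol Table 1, footnote f, says subjects return on Day 112 and Day 147 "for an assessment of warts to determine the durability of previous responses and/or LSRs".
- Protocol 10.2.1 and 10.7 follow unresolved adverse events until they resolve or stabilise, the subject is lost, or 30 days have passed since the end-of-study visit.
- Protocol 6.1.3.2 foresees subjects receiving fewer than four treatments, or attending outside the visit window, because of how long LSRs last.
- Protocol 5.0 and SAP 2.2.1 give Part B the primary objective of identifying the regimen with the best risk:benefit profile.

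**The concern.** The regimens differ in how long a vesicant stays on the skin, and Protocol 6.1.1 expects blistering as part of the effect: "Treatment regimens will be evaluated based on the requirement to form blisters in most patients". The same sentence couples this with a favourable safety and tolerability profile. For an agent that is meant to cause a skin reaction, the occurrence of a reaction is only part of the risk. Whether it goes away, and how quickly, is another part, and longer exposure could plausibly change it.

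If persistence is not tabulated, the risk side of the regimen choice rests on how many subjects reacted, how severely, and whether the event was related or serious. Two regimens with the same profile on those tables could leave different numbers of subjects with lasting pigment change, scarring or ulceration, and no regimen-level table would show it. Duration also matters outside safety, because the protocol itself links it to delayed or missed applications.

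**Working it through.** The documents state no figure on this point, so there is nothing to reproduce. The check has three parts.

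**1. What is collected against what is summarised**

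| Information on LSRs | Collected? | Planned table? |
|---|---|---|
| Occurrence by preferred term | Yes | Yes, SAP 10.3 |
| Peak severity | Yes; Protocol 10.3 records the highest level reached | Yes, SAP 10.3 |
| Relationship, seriousness, gender | Yes | Yes, SAP 10.3 |
| Number of events | Yes | Yes for all treatment-emergent events, Protocol 12.4 |
| Leading to study discontinuation | Yes | Yes for all treatment-emergent events, SAP 10.2 |
| Onset date | Implied (SAP 10.2 partial-date rule; Protocol 12.4 onset after end of study) | None by study day |
| Resolution and time to it | Follow-up required (Protocol 10.2.1, 10.7); stop-date and outcome fields not named | None |
| LSRs present at each visit | ERT in clinic at treatment visits and Day 84, 112 and 147, and by phone at 24 hours, 7 and 14 days after each treatment | Listing only, SAP 10.4 |

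The only split by time in SAP 10.2 is before and after a subject's COVID-19 affected date, which says nothing about duration. By contrast, durability of clearance has its own analysis in SAP 9.1.

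**2. What the late visits can show**

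Take Day 75, the last day for treatment without sponsor approval (Protocol 6.4), as the latest application.
- End-of-treatment visit, Day 84 to 92: 84 − 75 = 9 to 92 − 75 = 17 days later.
- Day 112 ± 7: 105 − 75 = 30 to 119 − 75 = 44 days later.
- Day 147 ± 7: 140 − 75 = 65 to 154 − 75 = 79 days later.

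For such a subject Day 84 can still catch fresh reactions. Days 112 and 147 separate these from lasting ones. Earlier last applications give longer intervals.

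**3. Size**

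Part B VP-102 subjects per regimen: 90 × 3/10 = 27. Part A adds 5 of 6 for a selected regimen, so 27 + 5 = 32. Matching placebo: 90 × 2/10 + 1 = 19.

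*How crowded could an any-event row be?* The nearest figures come from the childhood molluscum study VP-102-103 (Protocol 4.3.1): "A total of 29 subjects (88%) reported at least one treatment-emergent adverse event (TEAE), including expected LSRs such as blistering or erythema", that is 29/33 = 87.9%. Drug-related events, most of them LSRs, occurred in 21/33 = 63.6%. Used as assumed rates here, the numbers without an event are:
- 32 × (1 − 29/33) = 3.9, about 4 subjects;
- 32 × (1 − 21/33) = 11.6, about 12 subjects.

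The room for one regimen to show a higher any-event incidence is thus about 4 to 12 subjects, depending on the rate. This does not carry over to rarer preferred terms.

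*What could a persistence table show?* Purely as an illustration, suppose both regimens have 30/32 (93.8%) ever reacting, but at Day 112 an LSR is still present in 2/32 against 10/32. The exact 95% intervals are 0.8–20.8% for 6.3% and 16.1–50.0% for 31.3% (Fisher p = 0.022). A smaller contrast, 1/32 against 6/32, gives p = 0.10. With none persisting, the upper limit is 1 − 0.025^(1/32) = 10.9%.

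**The case against.** The strongest case against is that the plan delivers what it promised. The stated safety endpoint is incidence of adverse events, and no objective or endpoint names LSR duration. All comparisons are exploratory (SAP 8.6), and comparisons across regimens are observational (Protocol 12.3). LSR durability as a visit purpose appears only in footnote f; Protocol 6.4 and the synopsis mention only durability of treatment response. Listings allow case-by-case review. SAP 10.3 does not say its list of summaries is exhaustive, and neither is the list of adverse-event listing fields in Protocol 12.4.

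Most of this is correct, and it limits how strongly the point can be put. Four stronger readings are not supported.
- *That LSRs are reported by worst severity alone.* Relationship, seriousness and gender tables are also planned, with event counts and discontinuations for treatment-emergent events generally.
- *That late LSR data are discarded.* Only events with onset after the end-of-study visit are kept out of the tables (Protocol 12.4). An LSR that starts late is counted; what is missing is how long it lasts.
- *That incidence will sit near its ceiling and cannot separate the regimens.* The 88% is any event in children with molluscum, and 63.6% is closer to LSRs. Protocol 4.3.2 reports no treatment-related events in a 16-subject 24-hour cohort. Scarring, pigmentation change, erosion/ulceration and ring wart are distinct reaction types in SAP 10.3, and their rows need not fill up because blistering is common.
- *That the late visits exist to observe LSRs, or that regimens are picked simply because they blister.* LSR durability is one stated purpose of the visits, and blistering is one half of the criterion.

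The listings argument does not close the gap. A reader comparing about 32 subjects per regimen needs counts with denominators. A table added after database lock would be labelled post hoc under SAP section 5, so it is better specified now.

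**Conclusion.** The concern holds in a limited form. Every LSR summary listed in SAP 10.3 is a subject incidence without duration, resolution or presence by visit, and ERT data are listed only. The plan therefore gives a transient and a lasting reaction of the same type and grade equal weight in its regimen-level tables. Meanwhile the protocol follows these reactions to resolution, names their durability as one reason for two visits, and asks Part B to weigh risk against benefit.

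This is a gap in safety description. It does not bias the primary efficacy analysis, and the planned incidence tables remain useful, particularly for the rarer reactions. Its size cannot be fixed in advance because the documents give no persistence rate. The 4-to-12-subject headroom and the 2/32 against 10/32 example rest on assumed rates, on planned enrolment, and on pooling exactly 5 Part A VP-102 subjects per selected regimen. At that size the added tables would describe and could reveal a large difference; they would not exclude a moderate one.

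**What to change.** Add to SAP 10.3, in the Safety Population, by VP-102 regimen and matching placebo:

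- (a) number and percent of subjects with an LSR ongoing at Day 84, 112 and 147, by preferred term, with scarring, pigmentation change, erosion/ulceration and ring wart shown separately and the denominator at each visit stated;
- (b) LSR duration by preferred term, with unresolved events treated as censored, stating whether the unit is the episode or the subject's longest episode, since reactions can recur over up to four applications;
- (c) number and percent of subjects with an LSR unresolved at last contact, including the 30-day follow-up after the end-of-study visit.

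Derive these from adverse-event onset date, stop date and outcome. First confirm that the eCRF captures stop date and outcome, because the documents imply only the onset date. Show all three fields in the adverse-event listing. The adverse-event record keeps peak intensity only, so it can support presence at a visit but not severity at that visit; any severity-by-visit table would have to come from the ERT forms.

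The tables should be descriptive, with exact confidence intervals if wanted and no added testing between regimens. The cost is a few extra tables and some programming, with no new visits or assessments if the dates are already captured. If they are not, stop date and outcome need to be added to the form.
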